13.1.1 Analysis Populations

The following 2 analysis populations are planned for this study:

- Intent-to-treat (ITT) population: All subjects who are randomized and have documented one dose of IP at Visit 2 will be included in the ITT population. All efficacy analyses will be performed using the ITT population.
- Safety population: All subjects who are dispensed IP and reported administering at least one dose of IP will be included in the safety population. All safety analyses will be performed using the safety population.

Inclusion in the analysis populations will be determined prior to database lock.

If a subject is randomized incorrectly or is administered the incorrect IP, analyses of the ITT population will be based on the assigned treatment whereas all other analyses will be based on the actual treatment.

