4.2. Interim Analysis and Data Monitoring

No interim analyses or data monitoring are planned.

5. Analysis Populations

The following analysis populations are planned for this study:

- **All Subjects Population:** All subjects who sign an informed consent, participate in a Visit 1 (Screening), and are entered into the eCRF will be included in the All Subjects

population. The All Subjects population will be used for summaries of subject disposition.

- **Safety Population:** The Safety population includes all subjects who are dispensed IP and reported administering at least 1 dose of IP. The Safety population will be used for safety analyses. For analyses of the Safety population, each subject will be analyzed by the actual treatment received, even if it differs from the subject's randomized treatment assignment.
- **Intent-to-Treat (ITT) Population:** The ITT population includes all subjects who are randomized and have one documented dose of IP at Visit 2 (Baseline). The ITT population will be used for efficacy analyses. For analyses of the ITT population, each subject will be analyzed by their randomized treatment assignment, even if the subject did not receive the assigned treatment or did not follow the protocol until completion.

Assignment of subjects to populations will be confirmed at a blinded data review meeting to be held before the study database is locked. All protocol deviations that occur during the study will be considered for their severity/impact and will be taken into consideration when subjects are assigned to analysis populations.

6. General Issues for Statistical Analysis

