7.2. Protocol Violations and Deviations

Protocol deviations will be tracked, recorded, and reviewed prior to database lock, following the Protocol Deviation Guidance Plan for this study. The deviation list will be stored in the Remarque system and transferred to the biostatistics team for analysis.

Protocol deviations will be classified as “Important” or “Non-Important”. An important deviation poses a possible safety issue to the participant, or it has a potential impact on the statistical analysis of the clinical data. A non-important deviation is identified as any protocol deviation that does not meet the criteria for an important deviation.

Examples of important deviations include but are not limited to:

- Violation of inclusion/exclusion criteria
- Randomization or dosing error
- Use of prohibited medications
- Assessment conducted by unqualified personnel
- Missing baseline efficacy or safety assessments
- Lack of adherence to study drug dosing
- Controlled substance inappropriate handling

Examples of non-important deviations include but are not limited to:

- Lack of data collection due to subject non-compliance
- Subjects who fail to make scheduled visits
- Extension of screening period to clarify diagnoses or verify laboratory values
- Incorrect storage of study drug
- Failure to follow up on subjects who drop out

Subjects with at least 1 deviation classified as “Important” will be excluded from the PP Population. The final decision regarding classification of deviations and inclusion and exclusion

of subjects from the analysis populations will be based on a final listing of protocol deviations. Subject inclusion/exclusion in analysis populations will be determined during a blinded review meeting before study data are unblinded. Clinical and Biostatistics team members will provide input to the decision and the final composition of the analysis populations will be approved by the Sponsor.

Protocol deviations will be summarized by treatment group and overall subjects for the All Subjects population. Data will also be presented in a by-subject listing.

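### SAP Sections 5 and 7.2 permit protocol deviations to remove subjects from ITT, the only efficacy set, against its own definition, and they refer to a PP population that is never defined

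*SAP*

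**What the plan says.** **ITT definition.** SAP Section 5 lists three populations: All Subjects, Safety and ITT. ITT requires randomization and one documented dose at Visit 2. Subjects are analyzed as randomized "even if the subject did not receive the assigned treatment or did not follow the protocol until completion". Section 5 adds: "The ITT population will be used for efficacy analyses". Protocol 13.1.1 uses the same two membership conditions, assigns all efficacy analyses to ITT and analyzes by assigned treatment. It introduces its list with "The following 2 analysis populations are planned for this study", and the two are ITT and Safety.

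**Deviation sentences.** The paragraph after the SAP definitions has population assignment confirmed at a blinded meeting before database lock. It says that all deviations will be weighed for severity and impact and "will be taken into consideration when subjects are assigned to analysis populations". SAP Section 7.2 goes further: the final decision on classifying deviations, and on the inclusion and exclusion "of subjects from the analysis populations will be based on a final listing of protocol deviations".

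**PP.** SAP Section 7.2 says that subjects with at least one Important deviation "will be excluded from the PP Population". Its examples of Important deviations include "Use of prohibited medications", poor adherence to dosing, and randomization or dosing errors.

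**Intercurrent events.** SAP Table 3 handles prohibited-medication use before Week 4 by a hypothetical strategy. The subject stays in the analysis, the Visit 6 HAM-A score is treated as missing, and the change score is imputed.

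**The concern.** Two sets of rules govern membership of the same population. One has no deviation criterion and expressly keeps subjects who depart from the protocol. The other makes deviations an input to membership of every population. A data review team could follow either and say that it followed the SAP.

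The choice affects the primary result. Prohibited-medication use and poor adherence arise after randomization and may depend on how the subject is doing. Removing such subjects gives up the protection of randomization for the HAM-A comparison. Blinding the review stops anyone choosing by treatment. It does not stop the events themselves from being distributed differently between the arms.

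The PP sentence adds a smaller problem. It excludes subjects from a set with no definition, no stated analysis and no table. If such a set were built after unblinding, it could not be called pre-specified.

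**Working it through.** The plan gives no figure for this point, so the main check compares texts. The arithmetic that follows is illustrative and its inputs are labelled.

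**1. Is there a PP population?** It is named once, in SAP 7.2. It is not in SAP Section 5, the abbreviation list, the disposition shell (Table 14.1.1) or the populations listing shell (Listing 16.2.3.1, which shows Safety and ITT only). Every efficacy table in SAP Table 6 is ITT. Protocol 13.1.1 has no PP, and SAP Section 11 does not record one as a change from the protocol.

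**2. Do the two rules give the same ITT?**

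| Subject | ITT definition and Table 3 | Section 5 deviation sentence and Section 7.2 |
|---|---|---|
| Dosed at Visit 2, later uses prohibited medication | In ITT; Visit 6 score set to missing and imputed | Important deviation; membership open to review |
| Dosed at Visit 2, poor adherence | In ITT; observed score used | Important deviation; membership open to review |
| Randomized, no Visit 2 dose | Not in ITT | No conflict |

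The rules differ for the first two types of subject.

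**3. Effect on the missing-data switch.** SAP 6.1.4 uses group-mean imputation when the missing fraction in ITT is at most 0.05, and multiple imputation above that. With 40 subjects, 2/40 = 5.0% gives group-mean imputation and 3/40 = 7.5% gives multiple imputation. Two examples, assuming no other missing scores:
- Three prohibited-medication users kept in ITT: 3/40 = 7.5%, multiple imputation. The same three removed: 0/37 = 0%, no imputation.
- Two missing scores plus one removed subject whose score was observed: 2/39 = 5.1%, so the method switches to multiple imputation.

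**4. When would removal bias the comparison?** Suppose k₁ of 20 PH94B subjects and k₀ of 20 placebo subjects are removed, and their mean changes are g₁ and g₀ SD worse than those of the rest of their arm. Removal improves each arm mean by kg/20, so

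shift in the difference = (k₁g₁ − k₀g₀)/20.

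This is zero if removal is unrelated to response (g = 0) or if the two products are equal. With assumed values k₁ = 4, k₀ = 0 and g₁ = 0.5 to 1.0, the shift is 4 × 0.5/20 = 0.10 to 4 × 1.0/20 = 0.20 SD in favour of PH94B. The standard error of the unadjusted difference is √(2/20) = 0.32 SD.

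**5. Simulation of the planned ANCOVA.** The documents give 20 per arm and two-sided 0.05. Assumed: no true effect, baseline-outcome correlation 0.5, and k subjects removed at random from the worse-responding half of the PH94B arm. Ranges cover repeated runs.

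| k removed | Shift favouring PH94B (SD) | Rejection rate |
|---|---|---|
| 0 | 0 | about 5% |
| 1 or 2 | 0.03 to 0.07 | about 5% |
| 3 | 0.10 | about 6% |
| 4 | 0.14 | about 7% |

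When the same numbers are drawn from the pooled worse half without regard to arm, the shift is at most 0.005 SD and rejection is 4.9 to 5.1%.

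**The case against.** The strongest reply is that the authors never meant deviations to touch ITT. The only automatic exclusion rule names PP, so the general sentences may be leftovers from an abandoned PP set. SAP Section 5 uses soft wording. The sample reasons in Listing 16.2.3.1 for exclusion from ITT are lack of randomization or of a Visit 2 dose. Assignment is blinded and precedes lock, the study is described as exploratory, and SAP Section 1 requires unplanned analyses to be identified as such in the study report.

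Much of this stands. A reader might infer that subjects with Important deviations must be dropped from ITT because no other efficacy set exists. The documents do not say so: removal is permitted, not ordered, and Listing 16.2.3.1 suggests that ITT was meant to follow its dosing definition. A reader might also infer that any such removal biases the primary test even when blinded. That is too strong, because bias also requires the removals to differ by arm, and the documents give no rate or direction.

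The reply does not remove the contradiction. Section 7.2 is not softly worded, and neither sentence exempts ITT. SAP 6.1.5 has subjects with late visits judged case by case for inclusion in the analysis, so discretionary exclusion is contemplated elsewhere in the plan. Exploratory status does not settle it either: the primary test is run at 0.05, and the results are to guide Phase 2b and Phase 3.

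**Conclusion.** Wrong as written. The SAP permits post-randomization, deviation-based removal from its only efficacy population. That conflicts with the ITT membership rule in SAP Section 5 and Protocol 13.1.1, and with the Table 3 handling of prohibited-medication use. Separately, it refers to a PP population that does not exist in the plan.

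The conclusion rests on the texts, not on the simulation. The shift of about 0.10 to 0.14 SD and the type I error of about 6 to 7% describe an assumed one-sided worst case: 3 or 4 of 40 removed, all from the worse-responding half of PH94B. They are not a forecast. If removals do not differ by arm, the effect is about zero. If poor responders were removed mainly from placebo, the shift would go against PH94B.

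**What to change.** - **SAP Section 5:** replace the deviation sentence with: *A subject who meets the stated definition of the ITT or Safety population will not be removed from it because of a protocol deviation.* Tying the sentence to the definition matters. A flat statement that deviations never affect membership would clash with the Visit 2 dose requirement, since a missed first dose is itself a deviation.
- **SAP Section 7.2:** limit the blinded review to classifying deviations and confirming who meets the stated definitions. Delete the PP sentence. If a PP analysis is wanted, define PP in Section 5 as supportive, state its analysis and add its table before unblinding.
- **SAP 6.1.5:** bring the case-by-case rule for late visits into line with the new sentence.

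The cost is SAP wording only, plus one table shell if PP is kept. No new data or procedures are needed.

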6.1. Statistical Definitions and Algorithms

6.1.1. Baseline

Baseline for each study assessment (where applicable) is defined in Table 2.

Table 2: Baseline Definitions

Parameters	Baseline
Safety parameters including physical examinations and ECGs.	The last non-missing assessment before the first dose of study drug. This assessment will be at Visit 1 (Screening).
Safety parameters including vital signs, clinical laboratory tests, MADRS, and C-SSRS.	The last non-missing assessment before the first dose of study drug at Visit 2 (Baseline).
Efficacy parameters including HAM-A total score, ADNLM total score, and IADQ total score.	The last non-missing assessment before the first dose of study drug at Visit 2 (Baseline).

6.1.2. Adjustments for Covariates

For applicable efficacy models comparing change from baseline in efficacy measures of PH94B to placebo, the baseline value of the respective scale will be included as a covariate.

6.1.3. Multiple Comparisons

For the primary efficacy endpoint, group differences will be assessed at $\alpha = 0.05$. No adjustments will be made for comparison of secondary or exploratory efficacy endpoints as the study is exploratory.

[figure not shown]
6.1.4. Handling of Dropouts or Missing Data

Data will be included in the analysis according to the analysis visit windows described in Section 6.1.5.

Treatment of intercurrent events (ICEs) will be as described in Table 3. Briefly, subjects who withdraw from the study after treatment begins will be encouraged to complete an Early Termination Visit where all Visit 6 assessments will be performed. If the subject is lost to follow-up or otherwise unable to complete the Visit 6 assessments or if the subject uses a prohibited medication prior to the planned end of treatment, the Visit 6 HAM-A score will be set to missing. If the fraction of missing change from baseline to Visit 6 HAM-A total scores in the ITT population is ≤ 0.05 , missing change scores will be imputed with treatment group mean change scores for the primary efficacy analysis. If the fraction of missing change scores is greater than 0.05, multiple imputation of the change from baseline to Visit 6 HAM-A total scores will be carried out for the primary efficacy analysis. The fraction of missing change from baseline to Visit 6 HAM-A total scores will be computed as described in Section 6.1.7.2. The multiple imputation procedure will not impute individual HAM-A item scores or HAM-A total scores; only change from baseline to Visit 6 HAM-A total scores will be imputed. Other efficacy and safety data will not be imputed and will be analyzed as observed.

Table 3: Strategies for Intercurrent Events

ICE	Strategy for Addressing ICE
Treatment discontinuation following randomization but prior to Week 4.	While on Treatment Strategy The research objectives seek to understand the response to PH94B compared to placebo while subjects are actively using the study medication. Subjects who discontinue will undergo an Early Termination Visit and provide all Visit 6 outcome measures and safety assessments for the efficacy analysis.

ICE	Strategy for Addressing ICE

Treatment discontinuation following randomization but prior to Week 4 (subject lost to follow-up).
	
Hypothetical Strategy Measurement following ICE is unavailable and will be considered missing. Multiple imputation of the change from baseline to Visit 6 HAM-A scores will be carried out for the primary efficacy analysis using important subject variables and treatment assignment, if the fraction of missing change from baseline to Visit 6 HAM-A scores in the ITT population is greater than 0.05. In addition, the primary efficacy measure will be subjected to sensitivity analysis (complete case comparison and control-case using mean change from baseline HAM-A from the placebo group).

Use of prohibited medication prior to Week 4.
	
Hypothetical Strategy Measurement following ICE is not of interest and will be considered missing. Multiple imputation of the change from baseline to Visit 6 HAM-A scores will be carried out for the primary efficacy analysis using important subject variables and treatment assignment, if the fraction of missing change from baseline to Visit 6 HAM-A scores in the ITT population is greater than 0.05. In addition, the primary efficacy measure will be subjected to sensitivity analyses (complete case comparison and control-case using mean change from baseline HAM-A from the placebo group).

Abbreviations: HAM-A = Hamilton Anxiety Scale; ICE = intercurrent event.

The imputation approach has 2 broad components: i) the multiple imputation process for the placebo and PH94B data; and ii) the analysis method that will be used to draw inference regarding the primary estimand (Table 4), along with the method for combining the results across the multiply-imputed datasets. The primary estimand is defined in Section 8.1.

The imputation for the primary efficacy endpoint will be carried out in SAS using the fully conditional specification (FCS) method with a regression model approach (Carpenter and Kenward, 2013). The method assumes data are missing at random (MAR). Thus, subjects with missing values will have imputed values similar to other subjects with comparable observed profiles in the regression variables. The imputation will be carried out separately within each

treatment group. The regression model will include the following variables: baseline HAM-A total score, sex, age, LSAS total score, and analysis site. For each imputation process, a total of 25 complete datasets will be created. The random seeds to be used in the imputation process are 813616018 for the PH94B treatment group and 80521516 for the placebo treatment group.

The analysis method for the multiple imputation will match that described for the primary efficacy analysis in Section 8.1. Results from the multiply-imputed datasets will be combined using the standard Rubin's rules for multiple imputation (Little and Rubin, 1987) and will be done in SAS using PROC MIANALYZE.

Two sensitivity analyses will be performed to assess robustness of the multiple imputation results to changes in missing data assumptions. The sensitivity analyses include 1) a complete case analysis where only subjects with non-missing change from baseline in HAM-A total scores will be included, and 2) a control-case analysis, where missing change from baseline in HAM-A total scores will be imputed by the mean change from baseline for the placebo group. Sensitivity analyses are detailed in Section 8.1.1.

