13.1.1.1 Estimand Framework

The target of estimation to address the scientific question of interest (posed by the primary objective for this study):

In adults with AjDA, is the difference in mean change from baseline anxiety severity (as measured by HAM-A total score) greater for PH94B-treated subjects compared to placebo-treated subjects, after 4 weeks of treatment?

is defined by the following attributes:

1. Population: Adults with AjDA (as defined by inclusion and exclusion criteria).
2. Treatment: PH94B compared to placebo control.

3. Variable of interest: Change in subject reported severity of anxiety as measured by change from baseline in HAM-A total score using the SIGH-A, after 4 weeks of randomized treatment with the study medication.
4. Population-level summary measure: Difference in mean HAM-A total score between PH94B-treated and placebo-treated subjects after 4 weeks of treatment.
5. Anticipated intercurrent event: Treatment discontinuation prior to the planned assessment time frame.

Strategies for handling potential intercurrent events (ICE) are summarized in [Table 13-1](#).

Table 13-1: Strategies for Handling Intercurrent Events

ICE	Strategy for Addressing ICE
Treatment Discontinuation following randomization but prior to Week 4	While on Treatment Strategy The research objectives seek to understand the response to PH94B compared to placebo while subjects are actively using the study medication. Subjects who discontinue will undergo an Early Termination Visit and provide all Visit 6 outcome measures and safety assessments for the efficacy analysis.
Treatment Discontinuation following randomization but prior to Week 4 (subject lost to follow-up)	Hypothetical Strategy Measurement following ICE is unavailable and will be considered missing. Multiple imputation of Visit 6 efficacy measures using important subject variables and treatment assignment will be conducted and subjected to sensitivity analysis. (complete case comparison and assumption of treatment failure using 0 change from baseline HAM-A).
Use of prohibited medication prior to Week 4	Hypothetical Strategy Measurement following ICE is not of interest and will be considered missing. Multiple imputation of Visit 6 efficacy measures using important subject variables and treatment assignment will be conducted and subjected to sensitivity analyses (complete case comparison and assumption of treatment failure using 0 change from baseline HAM-A).

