from baseline to Visit 6 HAM-A total scores is greater than 0.05, change from baseline to Visit 6 HAM-A total scores will be imputed using the fully conditional specification approach to multiple imputation as described in Section 6.1.4. If the fraction of missing change scores is ≤ 0.05 , missing change from baseline to Visit 6 HAM-A total scores will be imputed with treatment group mean change scores.

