10.1. Coronavirus 2019 (COVID-19) Impact

The SARS-CoV-2 virus and variants may still be a threat and safety precautions may still be in place during study enrollment. To assess the impact of the COVID-19 pandemic on study procedures, study staff will complete the COVID-19 Impact questionnaire. Should a study visit be affected by COVID-19, study staff will record how the visit was affected (missed, abbreviated, delayed, performed remotely, or otherwise deviating from the planned format in the protocol) and which procedures were impacted. All COVID-19 protocol deviations will be provided in a separate listing. This listing will include the subjects, affected visits, and affected assessments.

11. Changes from Planned Analysis

Study staff will complete the Coronavirus 2019 (COVID-19) Impact questionnaire to assess the impact of the COVID-19 pandemic on study procedures. The COVID-19 Impact questionnaire is described in Section 10.1. All COVID-19 protocol deviations will be provided in a separate listing.

The ADNMs subscales exploratory endpoints analysis will not be completed as part of this SAP.

Physical examination and urinalysis results will not be summarized using descriptive statistics but will be listed.

The treatment failure sensitivity analysis will be replaced with a control-case sensitivity analysis that imputes the mean change from baseline to Week 6 in HAM-A total scores from the placebo group for missing change from baseline responses. This approach accounts for the potential for a

high placebo response.

12. References

- ASA. (2018) Ethical Guidelines for Statistical Practice. Prepared by the Committee on Professional Ethics, April 2018. <http://www.amstat.org/about/ethicalguidelines.cfm>
- Carpenter JR and Kenward MG. *Multiple Imputation and its Application (Statistics in Practice)*. Chichester, West Sussex, UK: John Wiley & Sons; 2013.
- Graham JW, and Olchowski AE, Gilreath TD. (2007) “How Many Imputations are Really Needed? Some Practical Clarifications of Multiple Imputation Theory.” *Prev Sci.* 2007;8(3): 206-213.
- ICH (1998). ICH Harmonised Tripartite Guideline. Statistical Principles for Clinical Trials E9; 1998. https://database.ich.org/sites/default/files/E9_Guideline.pdf
- Little R and Rubin D. (1987). *Statistical Analysis with Missing Data*, New York: Wiley.
- RSS. (2014) *The Royal Statistical Society: Code of Conduct*, 2014. <https://rss.org.uk/about/policy-and-guidelines/code-of-conduct/>.

13. Tables and Listings

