Note: Subjects are summarized by planned treatment. The HAM-A is a questionnaire used to assess anxiety and is completed by trained personnel. It consists of 14 items, each scored on a 5-point scale rating anxiety from "Not Present" to "Very severe". The HAM-A total score is the sum of the individual item scores. Baseline is defined as the HAM-A total score from Visit 2 (Baseline). Change from baseline is calculated as result – baseline result. Least squares mean, LS mean differences (treatment – placebo), 95% CIs, and P values were obtained from an ANCOVA model with change from baseline to Visit 6 in HAM-A total scores as the outcome, treatment group as a factor, and baseline HAM-A total score as a covariate.

[1] Visit 6 (End of Treatment/Early Termination) includes data from subjects who either completed Visit 6 (End of Treatment) or who discontinued from the study and completed an early termination visit.

Reference Listing: 16.2.6.1

Programming Note: If the rate of missingness in change from baseline to Visit 6 HAM-A total scores is >0.05 for the ITT population, then report the results of the multiple imputation analysis. Rate of missingness is computed as the number of ITT subjects missing change from baseline to Visit 6 HAM-A total scores divided by the total number of subjects in the ITT population. If reporting the results of the multiple imputation analysis, add the following text to the footnote before the sentence beginning with "Least squares mean...": "Multiple imputation was performed using conditional specification with baseline HAM-A total score, sex, age, LSAS total score, and analysis site. Twenty-five imputation datasets were created." If the rate of missingness in change from baseline to Visit 6 HAM-A total scores is <=0.05 but greater than 0, then add the following text to the footnote: "Missing change from baseline in HAM-A total scores were imputed with treatment group mean change scores."

AD-ST-33.06 Effective date: 12-Nov-2020

Table 14.2.1.1 (cont.)
ANCOVA Change from Baseline in HAM-A Total Scores by Visit – Primary Analysis
ITT Population

Study Visit [1] Statistic	PH94B (N=XX)		Placebo (N=XX)	
	Observed	CFB	Observed	CFB
Visit 3				
n	XX	XX	XX	XX
Mean (SD)	XX.X (XX.XX)	XX.X (XX.XX)	XX.X (XX.XX)	XX.X (XX.XX)
Median	XX.X	XX.X	XX.X	XX.X
Min, Max	(XX, XX)	(XX, XX)	(XX, XX)	(XX, XX)
Visit 4				
n	XX	XX	XX	XX
Mean (SD)	XX.X (XX.XX)	XX.X (XX.XX)	XX.X (XX.XX)	XX.X (XX.XX)
Median	XX.X	XX.X	XX.X	XX.X

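### With 5% or less of Visit 6 HAM-A changes missing, arm-mean filling followed by the ordinary ANCOVA raises the primary test's type I error to about 5.6% (one missing) or 6.2–6.3% (two missing)

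*SAP*

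**What the plan says.** SAP 6.1.4 splits the primary analysis by the fraction of ITT subjects without a Visit 6 HAM-A change. At 0.05 or below, "missing change scores will be imputed with treatment group mean change scores for the primary efficacy analysis". SAP 8.1 repeats the rule: "missing change from baseline to Visit 6 HAM-A total scores will be imputed with treatment group mean change scores". The programming note to Table 14.2.1.1 supplies the matching footnote: "Missing change from baseline in HAM-A total scores were imputed with treatment group mean change scores".

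Multiple imputation is used only above the threshold. SAP Table 3 makes it conditional: "if the fraction of missing change from baseline to Visit 6 HAM-A scores in the ITT population is greater than 0.05". The only variance rule for imputed data belongs to that branch: "Results from the multiply-imputed datasets will be combined using the standard" Rubin's rules. Nothing comparable is given for the mean-filled branch.

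The test is the ANCOVA of SAP 8.1, with treatment as factor and baseline HAM-A as covariate. On the error rate, SAP 6.1.3 states: "For the primary efficacy endpoint, group differences will be assessed at" α = 0.05. SAP 8.1.1.1 adds a complete-case ANCOVA as a sensitivity analysis whenever the primary endpoint has to be imputed.

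Protocol Table 13-1 has no threshold. For subjects lost to follow-up and for users of prohibited medication it says: "Multiple imputation of Visit 6 efficacy measures using important subject variables and treatment assignment will be conducted". SAP section 11 lists changes from the planned analysis, among them "The treatment failure sensitivity analysis will be replaced with a control-case sensitivity analysis", but not the 0.05 mean-fill rule.

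**The concern.** An arm mean put in place of a missing value is a computed quantity, not an observation. Without the covariate it leaves the arm mean, and so the estimated difference, exactly where it was. It adds nothing to the residual sum of squares, yet it raises n and the residual df by one. PROC MIXED cannot distinguish it from real data, so it reports more precision than the trial has.

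The primary p value and confidence interval are at stake. SAP 6.1.3 waives adjustment for secondary and exploratory endpoints but keeps 5% for the primary one, and this branch does not deliver 5%.

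**Working it through.** **Inputs from the documents.** Forty subjects randomized 1:1, so 20 per arm (protocol synopsis). Two-sided 0.05 (SAP 4.1 and 6.1.3). Threshold 0.05 (SAP 6.1.4). ANCOVA with treatment and baseline (SAP 8.1), so residual df = 40 − 3 = 37 with complete data.

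**Assumptions not in the documents.** All 40 are in the ITT population. Values are missing completely at random. The correlation between baseline and change is varied from 0 to −0.7. The SD cancels.

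**When the branch applies.** 1/40 = 0.025 and 2/40 = 0.05 qualify; 3/40 = 0.075 does not. At N = 39, 2/39 = 0.051 does not qualify. At N = 20, 1/20 = 0.05 still does. So two missing values are covered only if the ITT N is at least 40, and for N from 20 to 39 only one is.

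**Closed form.** Let a and b be the numbers missing per arm and m = a + b. Filling leaves the residual sum of squares unchanged (exact without the covariate, approximate with it). The reported residual variance divides it by 37, when 37 − m is correct. The reported variance factor is 1/20 + 1/20 = 0.1, when 1/(20−a) + 1/(20−b) is correct. Hence

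SE ratio (reported/correct) = √[ ((37−m)/37) × 0.1 / (1/(20−a) + 1/(20−b)) ]

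Type I error = 2·P(t with 37−m df > 2.0262 × ratio), where 2.0262 is the 97.5% point of t with 37 df.

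- None missing: ratio 1, type I error 5.00%, which reproduces the SAP's own figure.
- One missing: √(0.97297 × 0.1/0.10263) = √0.94803 = 0.9737. Cut-off 1.973 on 36 df: 5.62%.
- One per arm: √(0.94595 × 0.1/0.10526) = √0.89865 = 0.9480. Cut-off 1.921 on 35 df: 6.29%.
- Two in one arm: √(0.94595 × 0.1/0.10556) = √0.89616 = 0.9467. Cut-off 1.918 on 35 df: 6.33%.

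**Simulation of the planned ANCOVA.** 400,000 null trials per setting, at baseline–change correlations of 0, −0.3, −0.5 and −0.7. Ranges are across correlations.

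| Missing | Mean fill, type I error | Complete case, type I error | Mean fill, root-mean-square SE / true SD |
|---|---|---|---|
| none | 4.99–5.00% | same | 0.999–1.001 |
| 1+0 | 5.56–5.63% | 4.97–5.04% | 0.974–0.976 |
| 1+1 | 6.20–6.31% | 4.99–5.07% | 0.948–0.950 |
| 2+0 | 6.22–6.39% | 4.96–5.14% | 0.944–0.950 |

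Formula and simulation agree, and the type I error hardly depends on the assumed correlation. A separate run of 200,000 trials per cell gave 5.6% with one missing and 6.2–6.3% with two, against 4.9–5.0% for complete case.

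**The case against.** The strongest reply is that this matters little. At most two of 40 subjects are affected, and the excess is 0.6 to 1.3 percentage points. SAP sections 4 and 4.1 call the study exploratory, with tests meant to guide later trials. The trigger in SAP 8.1.1.1 also covers the mean-fill branch, so a correctly sized interval and p value would be reported beside the primary one. All of this stands and limits the weight of the point. It does not make the primary result correct.

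The protocol also leaves analysis details to the SAP (sections 13.1 and 13.1.4), and the SAP states its threshold openly. The missing entry in section 11 is therefore a gap in documentation, not concealment. It is still a gap, because that section does record another change to the same missing-data plan.

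A reader might go further in four ways that are not supported.

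- **That multiple imputation as specified would do no better.** In a simulation of the SAP's by-arm model with the standard Rubin df (60,000 null trials per cell), type I error was 5.5–5.6% with one missing, so there was no real gain. With two missing it was 5.1–5.2%, which is close to a full repair.
- **That the branch above 5% also needs changing.** The same model gave 3.7–4.9% with three to eight missing, so no inflation was shown there.
- **That the SE is a full 6% too small.** The average SE over the true SD was 0.940–0.946 with two missing, but that ratio is about 0.993 even with nothing missing. The shortfall due to filling is about 5%.
- **That this branch will probably supply the primary result.** Early Termination visits should limit missing values, but prohibited-medication users are set to missing as well, and the available text states no expected dropout rate.

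**Conclusion.** The mean-fill rule is wrong as written. With one missing value the primary SE is about 2.5% too small and the type I error about 5.6%. With two, which requires an ITT N of at least 40, the figures are about 5% and 6.2–6.3%. The nominal 95% interval then covers about 94.4% or 93.7–93.8%. These figures assume 20 per arm and values missing completely at random. The fault is small and conditional on one or two missing values, but it affects the primary inference, brings no compensating gain in information, and is not recorded as a departure from the protocol.

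**What to change.** In SAP 6.1.4, SAP 8.1 and the Table 14.2.1.1 programming note, delete the group-mean branch. At 5% missing or less, make the complete-case ANCOVA of 8.1.1.1 the primary analysis. In section 11, list this as a departure from protocol Table 13-1, which plans multiple imputation without a threshold. The sensitivity analyses in 8.1.1.1 and 8.1.1.2 are triggered by imputation being necessary. Below 5% it no longer would be, so the SAP should say whether the control-case analysis still runs there. No change to the multiple-imputation branch is asked for.

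The cost is SAP wording and a few lines of code, with no new data or visits. The confidence interval widens by about 3% with one missing (1/0.9737 = 1.027) or 5–6% with two (1/0.9480 = 1.055; 1/0.9467 = 1.056). This applies when baseline HAM-A explains little of the change. It widens less if the correlation is strong, because mean filling, which ignores the missing subject's baseline, then also makes the estimate noisier.
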